### **Last Contact Date:**

Last contact date for time-to-event analysis is calculated as follows:

- Ongoing Subjects (including subjects on-treatment and subjects that discontinued treatment but on-study): DCO date
- Subjects that discontinued study: The date of study discontinuation
- Subjects lost to follow up: The latest of last assessment, last visit, and last dose date

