7.9. Subject Retention

The primary objectives for the end of study analysis are to evaluate the effects of OCA compared with placebo on all-cause mortality and liver-related clinical outcomes. The overall study duration is event driven and will be determined by the time required to observe the prespecified adjudicated events for the clinical outcomes composite endpoint ([Section 7.8](#)). Therefore, it is very important that subjects continue to participate for the duration of the study to enable assessment of clinical outcomes.

Subjects may discontinue investigational product during the study; however, these subjects are expected to continue in the study until study termination and every effort will be made by the investigator to discuss subjects' continuation in the study. Investigators will emphasize to subjects the importance of their continuation in the study after withdrawal of investigational product by either continuing to attend regularly scheduled visits, allowing semi-annual telephone visits by the investigator, or by allowing the investigator to have continued access to the subjects' medical records to assess potential major adverse cardiovascular events (MACE) and liver-related clinical outcomes. The site staff will encourage subjects to adopt an option that allows for the most data moving forward. Subjects will be asked to provide both personal and primary physician(s) contact information who can provide information to the investigator about the clinical/medical status on the subjects' behalf. Additional information is described in [Section 8.2.1](#).

Please refer to specific strategies and procedures that will provide additional information to facilitate subject retention as described in a separate Subject Retention Plan.

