8.2.1. Other Reasons for Discontinuation of Investigational Product

Subjects who discontinue investigational product are expected to continue in the study until the end of the study or at the discretion of the Sponsor. With the exception of liver transplant, if a subject experiences a suspected or confirmed clinical outcomes event, he or she should continue the regular visit schedule and continue taking investigational product as long as the Investigator assesses it as safe. Subjects who discontinue investigational product prior to termination of the study need to also continue to follow the regular visit schedule through to study closure. In general, subjects should be strongly encouraged to both stay on investigational product and remain in the study until study termination. Specific strategies to encourage continued subject participation in the study will be outlined in a Subject Retention Plan. Early termination procedures should only be conducted if the subject withdraws consent (see [Section 9.9.9](#)).

The following events are considered appropriate reasons for a subject to discontinue investigational product; however, these subjects are expected to continue in the study until study termination (or at the discretion of the Sponsor):

- The Investigator or Sponsor considers that it is advisable or in the best interest of the subject.
- The occurrence of clinical or laboratory AEs considered by the Investigator to be clinically important.
- Modification of consent:
 - Consent may be modified to discontinue study visits but allow semi-annual telephone contact of subject, subject's primary care physician, or personal contacts who can provide information on behalf of the subject by the investigator
- Consent may be modified to discontinue study visits or semi-annual telephone contact but allow continued access to medical records to assess for potential major adverse cardiovascular events (MACE) and liver-related clinical outcomes
- Withdrawal of consent:
 - Consent may be fully withdrawn

The Investigator must notify the Medical Monitor as soon as possible when a decision to discontinue a subject from treatment is made or when any subject prematurely withdraws from the study.

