16.6.1. Time to Event Endpoints

For the time-to-event analyses, including the primary clinical outcomes composite endpoint, only adjudicated events (including biopsy confirmed progression to cirrhosis) will be included. Subjects who do not experience an adjudicated event will be censored at the time of their last contact. Sensitivity analyses will be described in the SAP.

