Time-to-event data will be summarized using Kaplan-Meier (KM) methodology using 25th, 50th (median), and 75th percentiles with associated 2-sided 95% CIs, as well as the percentage of censored observations. KM estimates will be plotted as a “survival curve” for each treatment group, with the number at risk identified. In addition, time-to-event data will be summarized with descriptive statistics for those subjects with an event. Subjects who do not experience an event will be censored. Subjects who do not experience an event will be censored at the date of last contact for clinical outcome endpoints and will be censored at the earliest date of last dose date+30 days, end of study, death date or date cut-off date for treatment-emergent adverse events (TEAEs). The censor date for time to resolution events will be the earliest date of end of study, death date or date cut-off date.

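### Censoring every ongoing subject at the data cut-off credits event-free time in which MELD and biopsy events had no scheduled means of detection; this biases the hazard ratio if limited follow-up differs by arm

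*SAP*

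**What the plan says.** The protocol's rule for the time-to-event endpoints (Section 16.6.1) is: "Subjects who do not experience an adjudicated event will be censored at the time of their last contact". It does not define last contact.

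SAP Section 4 repeats the rule: "Subjects who do not experience an event will be censored at the date of last contact for clinical outcome endpoints". SAP Appendix A then defines the date, introduced by "Last contact date for time-to-event analysis is calculated as follows":

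- Still on study: "Ongoing Subjects (including subjects on-treatment and subjects that discontinued treatment but on-study): DCO date".
- Left the study: the date of study discontinuation.
- Lost: "Subjects lost to follow up: The latest of last assessment, last visit, and last dose date".

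Only the first category receives a date that need not correspond to any contact.

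The protocol allows reduced follow-up. Section 8.2.1 states: "Consent may be modified to discontinue study visits but allow semi-annual telephone contact of subject". It also allows a record-review mode with neither visits nor calls. Section 7.9 treats both as continuing in the study, by "allowing semi-annual telephone visits by the investigator, or by allowing the investigator to have continued access to the" medical records. Of subjects who stop investigational product for such reasons, Section 8.2.1 says "these subjects are expected to continue in the study until study termination (or at the discretion of the Sponsor". Table 6 (Section 9.9.9) gives both modes one combined end-of-treatment and end-of-study visit near the last dose. Its footnote limits later data essentially to what adjudication needs.

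**The concern.** A data cut-off is an administrative date. Censoring there is sound when each subject's status is known to that date for every component of the composite. For two groups the plan does not ensure this.

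The first is subjects who have stopped responding but have not yet been classed as lost. Protocol Section 8.2.3 sets no time limit for that decision, so they can be coded as ongoing when the data are cut.

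The second is telephone-only and record-only subjects. MELD of 15 or more is calculated from visit laboratory samples, and histological cirrhosis is dated by biopsy (SAP Section 6.4.7.1). Neither is scheduled for these subjects after the combined visit, yet they stay in the risk set to the cut-off, possibly for years.

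Risk time without the matching events lowers the apparent event rate. If one arm has more of it, the primary hazard ratio moves in that arm's favour, at the interim and at the end.

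**Working it through.** **Plan figures.** The interim is at 66% of 288 events: 0.66 × 288 = 190.08, which agrees with the SAP's 190 (Section 6.4.1). Stage 2/3 subjects in the two primary arms: 2085 × 2/3 = 1390, or 695 per arm. The derivation of 288 is not in the text available, so it was not rebuilt.

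**Attending subjects.** Visits after Month 18 are 6 months apart and a month is 28 days (Protocol Section 9.9.1), so the gap from last visit to cut-off is at most about 6 × 28 / 7 = 24 weeks. It averages about 12 weeks if the cut-off falls at random between visits. As a share of follow-up this is 12 / 52.18 / 3 = 7.7% at 3 years and 12 / 52.18 / 6 = 3.8% at 6 years. The visit schedule is the same in all arms. At the final analysis the end-of-study visit (Protocol Section 7.8) largely closes the gap, so it matters mainly at the interim.

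**Telephone-only and record-only subjects.** The documents give no share for these modes, so their effect can only be illustrated. Simulation assumptions: 695 per arm; 3.5% annual hazard; 4-year accrual; move to limited follow-up at a time uniform over 0.25-4 years, unrelated to prognosis; 50% or 80% of later events unrecorded; cut-off at the 288th recorded event; one log-rank test at two-sided 0.03; 1,500 runs. The true hazard ratio is 1, so the nominal false-win rate for OCA is 0.03 / 2 = 1.5%, with simulation error √(0.015 × 0.985 / 1500) = 0.3 percentage points. The right-hand columns stop events and censoring together at the last full assessment.

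| Limited follow-up, placebo / OCA | Later events missed | HR, cut-off rule | False win | HR, last full assessment | False win |
|---|---|---|---|---|---|
| 10% / 10% | 50% | 1.00 | 1.4% | 1.00 | 1.3% |
| 10% / 10% | 80% | 1.00 | 1.2% | 1.00 | 1.0% |
| 5% / 10% | 50% | 0.98 | 1.8% | 1.00 | 0.9% |
| 5% / 10% | 80% | 0.97 | 3.0% | 1.00 | 1.7% |
| 10% / 20% | 50% | 0.96 | 3.1% | 1.00 | 1.1% |
| 10% / 20% | 80% | 0.94 | 5.3% | 1.00 | 1.0% |
| 5% / 20% | 50% | 0.94 | 4.6% | 1.00 | 2.0% |
| 5% / 20% | 80% | 0.91 | 9.6% | 1.00 | 1.6% |

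With a true hazard ratio of 0.75 and unequal shares, the cut-off rule gave 0.68-0.74 and the last-full-assessment rule 0.75-0.76.

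**Does a better contact date suffice?** A second null simulation used 400,000 per arm, 3.5 events per 100 person-years, 4-year accrual, cut-off at year 8, 15% limited follow-up on placebo against 20-30% on OCA, and 50-70% of events detectable only in clinic. The standard error of log HR was about 0.017 at 40,000 per arm, hence about 0.017 / √10 = 0.005 here.

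- Cut-off rule: HR 0.987 to 0.923.
- Latest documented contact: the same to within 0.001, because a subject called every 6 months always has a recent contact.
- Last clinic assessment: about 1.00.

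For silent subjects still coded as ongoing, the latest-contact rule does help, by about 0.01-0.02 in the hazard ratio, again on assumed shares.

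**Scale.** With 288 events and equal allocation the standard error of log HR is about 2 / √288 = 0.118. A null value of 0.923 is a shift of |ln 0.923| / 0.118 = 0.080 / 0.118 = 0.68 standard errors; 0.987 is 0.013 / 0.118 = 0.11.

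**The case against.** The strongest reply is that stopping drug is not stopping visits. Protocol Section 7.7 and Table 4 tell discontinuers to keep the regular visit schedule, and reduced follow-up needs a separate change of consent. The pruritus discontinuations quoted from earlier studies are few: one in the 25 mg study, and 0, 0, 2 and 5 on placebo, 10, 20 and 40 mg in another (Section 5.3). This stands. A reader might infer that the rule favours OCA; the documents give no frequency of limited follow-up, by arm or overall, so no direction is established.

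It is also tempting to say that nobody observed the credited time. That goes too far: calls and record review exist to find outcomes and can capture deaths, transplants and hospitalisations. Laboratory tests or biopsies done in ordinary care may also surface. The gap is in scheduled MELD and histology.

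Nor does the SAP contradict the protocol, which leaves last contact undefined. It makes the term operational, in a way that needs no contact. Whether telephone-only and record-only subjects count as ongoing is not spelled out: Protocol Sections 7.9 and 8.2.1 point to yes, while their completed combined end-of-study visit could lead a programmer to code them as having left.

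Finally, a reader might conclude that no sensitivity analysis is planned. That cannot be said: SAP Section 6.2.3 is listed and cited, but its text is not in the version available. The retention and performance plans, also unseen, may include status checks.

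**Conclusion.** The concern holds as a conditional one. The SAP's definition credits event-free time to the cut-off without requiring that status be known there, and this reaches the primary composite. For attending subjects the effect is a gap of at most about 24 weeks, relevant mainly at the interim.

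For silent, telephone-only and record-only subjects the hazard ratio is distorted only if their share differs by arm. It would favour OCA if limited follow-up is more common there, and placebo in the reverse case. Under assumed shares of 15% against 20-30%, with 50-70% of events detectable only in clinic, the null hazard ratio is about 0.92-0.99. With equal shares there is no bias.

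These figures rest on assumed shares, hazard and missed-event fractions, and on the move to limited follow-up being unrelated to prognosis. The false-win rates come from a single fixed test, not the group sequential boundary. A better contact date corrects the silent subjects but leaves the MELD and biopsy ascertainment bias almost untouched.

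**What to change.** 1. In SAP Appendix A, replace the cut-off default for ongoing subjects with the latest documented visit, call, record review or assessment on or before the cut-off. Alternatively, keep the cut-off only for subjects whose status at that date is confirmed by a documented check. State that telephone-only and record-only subjects fall under this rule. At the same time reconcile the treatment of study discontinuation: Appendix A uses the discontinuation date, while Section 2.3.2.1 uses the last available assessment.

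2. Pre-specify, or confirm in SAP Section 6.2.3, a sensitivity analysis of the primary endpoint that censors each subject at the last clinic assessment at which all components could be ascertained. Apply the same limit to events and to censoring; counting later events while censoring the others early would create the opposite bias. Report the number of telephone-only and record-only subjects and their person-time by arm.

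The cost is mainly SAP wording before unblinding. Dates of event-free calls and record reviews must be available, and Protocol Table 6 does not show that they are collected, so a small data-collection change may be needed. Total follow-up becomes slightly shorter. In the sensitivity analysis some later deaths and hospitalisations are not counted, and it assumes that the move to limited follow-up is unrelated to prognosis, so it should support the primary analysis and not replace it.

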### **Standard Calculations:**

Variables requiring calculation will be derived using the following formulas:

- Days – A duration expressed in days between one date (*date1*) and another later date (*date2*) will be calculated using the following formulas:
  - duration in days =  $date2 - date1 + 1$ , where  $date1 \geq \text{first dose date}$
  - duration in days =  $date2 - date1$ , where  $date1 < \text{first dose date}$
- Months – A duration expressed in months is calculated as the number of days divided by 28 for study-related duration.
- Years – A duration expressed in years between one date (*date1*) and another date (*date2*) is calculated using the following formulas:
  - duration in years =  $(date2 - date1 + 1) / (\# \text{ of days in the year})$ , where  $date1 \geq \text{first dose date}$

duration in years = (date2 – date1)/ (# of days in the year), where date1 < first dose date

# of days in the year = 336 is based on 12 months with 28 days per month for study-related duration calculations.

# of days in the year = 365.25 for age, years since NASH diagnosis, patient-year and other duration calculations that are not study-related

- Age – Age is calculated as the number of years from the date of birth (*DOB*) to the specified date, eg, date of informed consent (*DOIC*). If the month of *DOIC* < month of *DOB* or the month of *DOIC* = *DOB* and the day of *DOIC* < day of *DOB*, then the following formula is used:

age (years) = year of *DOIC* – year of *DOB* – 1.

Otherwise, the following formula is used:

age (years) = year of *DOIC* – year of *DOB*.

If only Year is provided in *DOB* then use July 1 for the month and day

- Date of birth in Year format: To convert the date of birth format from Day/Month/Year to Year only, the following will be applied:

If birth date before July 1, then use year of birth = reported year - 1

If birth date after July 1, then use year of birth = reported year

- Height – Height entries made in inches (in) are converted to centimeters (cm) using the following formula:

height (cm) = height (in) × 2.54

- Weight – Weight entries made in pounds (lb) are converted to kilograms (kg) using the following formula:

weight (kg) = weight (lb) / 2.2046

- Temperature – Temperature entries in degrees Fahrenheit are converted to degrees Celsius using the following formula:

temp (degrees Celsius) =  $5 / 9 \times (\text{temp [degrees Fahrenheit]} - 32)$

- Body Mass Index (BMI) – BMI is calculated using height (cm) and weight (kg) using the following formula:

BMI (kg/m^2) = weight (kg) / ([height (cm)/100])

- Change from Baseline – Change from Baseline will be calculated as:

Change = post Baseline value – Baseline value

- Percentage change from Baseline – Change from Baseline will be calculated as:

Percentage change from Baseline =  $([\text{post Baseline value} - \text{Baseline value}] / \text{Baseline value}) \times 100$

- NAS (0-8) is derived as the sum of three components of standardized histologic feature scoring system for liver biopsies:  
NAS = steatosis score (0-3) + lobular inflammation score (0-3) + hepatocellular ballooning score (0-2)
- MELD score will be reported as an integer and is derived using the following formula (OPTN):

Candidates who are at least 12 years old receive an initial MELD(i) score equal to:

$0.957 \times \text{Loge}(\text{creatinine mg/dL}) + 0.378 \times \text{Loge}(\text{bilirubin mg/dL}) + 1.120 \times \text{Loge}(\text{INR}) + 0.643$  Laboratory values less than 1.0 will be set to 1.0 when calculating a candidate's MELD score.

The maximum MELD score is 40. The MELD score derived from this calculation will be rounded to the tenth decimal place and then multiplied by 10.

For candidates with an initial MELD score greater than 11, the MELD score is then re-calculated as follows:

$$\text{MELD} = \text{MELD}(i) + 1.32 \times (137 - \text{Na}) - [0.033 \times \text{MELD}(i) \times (137 - \text{Na})]$$

Sodium values less than 125 mmol/L will be set to 125, and values greater than 137 mmol/L will be set to 137. MELD Na will be rounded to the nearest integer.

MELD Score computed from lab results for samples collected in the same visit date. Any exceptional cases, prior to protocol version X, will be documented

- The eGFR will be calculated using the Chronic Kidney Disease Epidemiology Collaboration (CKD-EPI) 2021 equation ([CKD-EPI Chronic Kidney Disease Epidemiology Collaboration 2021](#)):

[figure not shown]
$$eGFR(\text{mL}/\text{min}/1.73 \text{ m}^2) = 142 \times \left(\frac{S_{cr}}{\alpha}\right)^{-0.241} \times 0.993^{age} \times 1.012 \text{ if } S_{cr} \leq \alpha \text{ for female}$$

$$= 142 \times (S_{cr}/\alpha)^{-1.200} \times 0.993^{age} \times 1.012 \text{ if } S_{cr} > \alpha \text{ for female}$$

$$= 142 \times (S_{cr}/\alpha)^{-0.302} \times 0.993^{age} \text{ if } S_{cr} \leq \alpha \text{ for male}$$

$$= 142 \times (S_{cr}/\alpha)^{-1.200} \times 0.993^{age} \text{ if } S_{cr} > \alpha \text{ for male}$$

Where Scr (standardized serum creatinine) = mg/dL,  $\alpha = 0.7$  if female and  $0.9$  if male, age = years.

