9.9. Visit Procedures

9.9.1. Visit Windows

Visits should be based on Day 1 (not on the prior visit) unless stated otherwise. For example, Month 3 should ideally occur 3 months (± 2 weeks) following Day 1. A month is defined as 4 weeks (ie, 28 days). The visit windows are as follows:

Table 5: Visit Windows and/or Intervals

Visit or Procedure	Visit Window and/or Interval
Screening	Visit(s) are to occur ≤12 weeks before Day 1. Subjects will be enrolled in the study when informed consent is obtained.
Day 1	This is the day of randomization and day of the first dose of investigational product. On-treatment visit scheduling should be calculated from this point going forward unless stated otherwise. ██████████ ██████████ measurements may be completed as soon as Screening Visit 1 through Day 1.
Month 1	±1 week (7 days)
Months 3 through 15	±2 weeks (14 days)
Month 18	±6 weeks to + 2 weeks (56 days)
Semi-Annual/Annual (Months 24, 30, 36, 42, 54, 60, 66, 72, 78 and continued every 6 or 12 months until the EOS)	±2 weeks (14 days)
Month 48	±4 weeks (28 days)
EOS	±2 weeks (14 days) relative to the EOS date announced by the Sponsor and the visit should be done as soon as possible upon study discontinuation
EOT	Visit should be done as near as possible to last dose taken

EOS = end of study; EOT = end of treatment

Sites should attempt as much as possible to schedule each visit within a 100-day window during the first 18 months of treatment and within the scheduled visit window per protocol based on the Day 1 Visit. If a known visit schedule departure is planned for a time frame greater than 100 days from previous visit during the first 18 months of treatment, an unscheduled bottle should be proactively dispensed and provided to the subject.

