### 4.3. Visit Windows

[figure not shown]
Visit windows will be defined around the target date of the visit as planned in the protocol. Day 1 is the first day of receiving investigational product (OCA or placebo). Month 18 (Week 72) biopsy window is Week 60 to Week 96. For all assessments, other than biopsy, each visit window will have the target date as the center and the lower bound is the midway between the target date of this window and the preceding one. The upper bound is the midway between the target date of the current window and the following one. If more than one assessment is collected within a window, then the assessment closest to the target date will be selected. If more than one assessment with the same distance from the target date, then the last assessment will be used. “Last” will be based on sorting by date, time, record number/sequence number. [Appendix B](#) shows the visit windows of each visit up to Month 78.

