##### **6.4.7.1. Time to Each Component of the Clinical Outcome Endpoint**

[figure not shown]
[figure not shown]
Time to each of the following components of the clinical outcome endpoint and time to HCC will be analyzed by treatment group using ITT and Full Efficacy Analysis Populations:

[figure not shown]
- Death: date of death
- Liver transplant: date of first liver transplant
- MELD score  $\geq 15$ : date of first occurrence of MELD  $\geq 15$
- Hospitalization (as defined by an inpatient stay of 24 hours or greater) for new onset or recurrence of: variceal bleed, encephalopathy (as defined by a West Haven grade  $\geq 2$ ), spontaneous bacterial peritonitis (confirmed by diagnostic paracentesis): date of earliest hospitalization admission.
- Ascites secondary to cirrhosis and requiring medical intervention: date of earliest ascites start date as an adverse event that required medical intervention.
- Histological progression to cirrhosis: date of biopsy

[figure not shown]
Only adjudicated events (and biopsy confirmed progression to cirrhosis) will be included in the analyses. The time to event of each of the components of the clinical outcome endpoint are defined as follows:

[figure not shown]
- Time to death (all-cause), first MELD score  $\geq 15$  and first liver transplant will be calculated in days as the date of the event minus the date of randomization plus 1. Subjects who do not experience an event will be censored at the date of last contact.
- Time to the first occurrence of onset of ascites (secondary to cirrhosis and requiring medical intervention), will be calculated in days as the first time for onset of the ascites minus the date of randomization plus 1.
- Time from randomization to the date of biopsy confirming histological progression to cirrhosis will be calculated in days as the date of the diagnosis minus the date of randomization plus 1. Subjects who do not experience an event will be censored at the date of last contact.

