### 10.1. Extent of Exposure

The extent of exposure will be summarized both continuously using descriptive statistics and categorically (n and % for  $\leq 4$  weeks,  $>4$  and  $\leq 12$  weeks,  $>12$  and  $\leq 24$  weeks,  $>24$  and  $\leq 36$  weeks,  $>36$  and  $\leq 48$  weeks,  $>48$  and  $\leq 72$  weeks,  $>72$  and  $\leq 96$  weeks,  $>96$  weeks  $\leq 120$  weeks;  $>120$  weeks  $\leq 144$  weeks,  $>144$  weeks  $\leq 168$  weeks,  $>168$  weeks  $\leq 192$  weeks). After Month 48 (Week 192) until the end of the study, exposure will be presented by 48 weeks periods.

Extent of exposure (days) to investigational product will be calculated as follows:

- Exposure to investigational product =  $\{[(\text{Date of last investigational product dose} - \text{Date of 1}^{\text{st}} \text{ investigational product dose}) + 1] - \text{Total duration of temporary investigational product discontinuation, interruption, drug holidays and/or missed doses}\}$

The duration of each incidence of temporary investigational product discontinuation will be calculated as follows:

- Duration of temporary discontinuation, interruption, and/or missed doses of investigational product =  $(\text{Date of restart of investigational product} - \text{Date of temporary discontinuation, interruption, drug holidays and/or missed doses of investigational product}) + 1$ .

The total duration of temporary investigational product discontinuation is the sum duration of temporary discontinuation, interruption, and/or missed doses of investigational product over each incidence of discontinuation / interruption.

Total investigational product (mg) exposed to subject will be calculated by adding the doses taken by a subject during the study and will be summarized using descriptive statistics.

A summary of subjects who had an at least one temporary investigational product interruption, discontinuation, and/or missed doses (including drug holiday) during the study will be provided in terms of frequency count (n) and percentages (%) and mean duration of the interruptions/missed doses. This summary will be presented by reason of interruption as specified in the eCRF.

Subject's overall compliance (%) with investigational product will be calculated as follows:

- $(\# \text{ of tablets consumed during study} / \# \text{ of tablets expected to be consumed during study}) * 100$

where # of tablets consumed during study = # of tablets dispensed- # of tablets returned or

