#### 10.5.6. Renal Function Evaluations

Summary statistics for absolute values, change from baseline, and percent change from baseline to each on-study evaluation visit, as well as worst and last postbaseline values, will be presented for eGFR, serum creatinine, and urinary albumin to creatinine ratio as specified in [Table 8](#). The summary will also be repeated for baseline CKD stage, baseline diabetes status (history of diabetes mellitus at baseline or on antidiabetic medications at baseline with indication for diabetes mellitus or baseline HbA1Cc  $\geq 6.5\%$ ), and baseline fibrosis stage. The 95% CIs for the difference in mean change will be also presented.

Annualized change in eGFR (mL/min/1.73 m^2/yr) will be summarized descriptively. The proportion of subjects that experience rapid eGFR decline (defined as  $>4$  mL/min/1.73 m^2/yr) will be presented.

Plots will be created to show mean laboratory (kidney function) data change from baseline over time for eGFR, serum creatinine, and as appropriate other markers of kidney function or injury such as Albumin to creatinine ratio. An additional plot for the percent change from baseline over time will be created only for serum creatinine.

Descriptive statistics for eGFR will be presented for subgroups by baseline CKD stage, baseline diabetes status, and baseline fibrosis stage.

Renal safety parameters serum creatinine and eGFR will also be utilized to present analyses of the worst change from baseline at any post-baseline visit, including risk differences and 95% CIs (using CMH method). The following change from baseline categories will be analyzed:

- Creatinine ( $\geq 1.5$  x BL,  $\geq 2.0$  x BL,  $\geq 3.0$  x BL)
- eGFR ( $\geq 25\%$  decrease from BL,  $\geq 50\%$  decrease from BL,  $\geq 75\%$  decrease from BL)

A listing will be created to display subjects with any post-baseline serum creatinine value  $\geq 2.0$  x BL or eGFR  $\geq 50\%$  decrease from BL.

A summary will also be provided based only on the last on-treatment measurements recorded for serum creatinine and eGFR, including risk differences and 95% CIs (using CMH method). The following change from baseline categories will be analyzed:

- Creatinine ( $\geq 1.5$  x BL,  $\geq 2.0$  x BL)
- eGFR ( $\geq 25\%$  decrease from BL,  $\geq 50\%$  decrease from BL)

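### SAP Appendix A uses a 336-day year for study-related durations but 365.25 days for patient-years, so a time expressed in study years runs 8.7% over calendar time and does not tie to the patient-year rates

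*SAP*

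**What the plan says.** SAP Appendix A (Standard Calculations) sets the formulas that derived variables are to use. For months: "A duration expressed in months is calculated as the number of days divided by 28 for study-related duration". For years it gives two divisors. The first is for study-related durations: "336 is based on 12 months with 28 days per month for study-related duration calculations". The second is "365.25 for age, years since NASH diagnosis, patient-year and other duration calculations that are not study-related". The term study-related is not defined.

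The 28-day month comes from the protocol's section on visit windows (9.9.1): "A month is defined as 4 weeks (ie, 28 days". The SAP's visit labels agree with it. Section 4.3 has "Month 18 (Week 72) biopsy window is Week 60 to Week 96", and Section 10.1 has "After Month 48 (Week 192) until the end of the study, exposure will be presented by 48 weeks periods".

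Some outputs carry their own unit:
- Times to the components of the clinical outcome endpoint (Section 6.4.7.1) are in days; for death, MELD and transplant the time "will be calculated in days as the date of the event minus the date of randomization plus 1".
- Extent of exposure (Section 10.1) is in days, with categories in weeks.
- Subject exposure years in the exposure-adjusted incidence rates (Section 10.4) and patient-years on study in the pruritus analysis (Section 10.4.1) are divided by 365.25.

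Others do not. Sections 4 and 6.4.4.2 (Kaplan-Meier percentiles for the primary composite) and Section 10.4 (Kaplan-Meier times for adverse events of special interest) state no time unit. Section 10.4.9.1 plans an annualised adjudicated cardiovascular event rate without a divisor. Section 10.5.6 plans an annualised eGFR change, followed by "The proportion of subjects that experience rapid eGFR decline", defined as a loss of more than 4 mL/min/1.73 m2 per year, again without a divisor.

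**The concern.** A 28-day month is a sound way to name visits. Appendix A turns it into a unit conversion for results. Readers take a year in a report to be a calendar year, and the protocol's own planning figures (about 10 years in total, about 4 years minimum follow-up) carry no 28-day or 336-day qualifier.

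The clearest clash is inside Section 10.4. For a subject with an event, the exposure-years run from first dose to onset and are divided by 365.25. The Kaplan-Meier time to onset uses the same two dates. If that time is shown in years, Appendix A points to 336. The same subject and the same event would then have two different numbers of years in neighbouring tables.

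For the eGFR output the choice of divisor also changes who is counted, because the result is compared with a fixed cut-off per year.

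**Working it through.** **Inputs.** 28 days per month and 336 days per year for study-related durations; 365.25 days per year for patient-years (all SAP Appendix A). Month 18 = Week 72 (Section 4.3). Month 48 = Week 192 (Section 10.1). eGFR cut-off of 4 mL/min/1.73 m2 per year (Section 10.5.6).

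**The plan's own figures reproduce.** 12 × 28 = 336. 18 × 28 / 7 = 72 weeks. 48 × 28 / 7 = 192 weeks. The convention is internally exact.

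**Size of the discrepancy.**
- Years: 365.25 / 336 = 1.0871, so 8.7% longer than calendar time.
- Months: (365.25 / 12) / 28 = 30.4375 / 28 = 1.0871, the same factor.
- Four calendar years: 4 × 365.25 = 1461 days; 1461 / 336 = 4.35 study years.
- Ten calendar years: 3652.5 / 336 = 10.87 study years.
- In the other direction, Month 48 = 1344 days = 4.00 study years, but 1344 / 365.25 = 3.68 calendar years.

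**One interval, two values.** For an event with (onset − first dose + 1) = 1461 days, the exposure-years in Section 10.4 are 1461 / 365.25 = 4.00. A time to onset in years under Appendix A is 1461 / 336 = 4.35.

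**Annualised outputs, if they follow the 336-day rule.**
- eGFR: a loss of 4 per 336 days is 4 × 365.25 / 336 = 4.35 per calendar year. Subjects losing between 4 and 4.35 per calendar year would not be flagged.
- How many subjects that is depends on the spread of slopes, which the documents do not give. Assume normal slopes with mean −1.5 and SD 3.5. The flagged share is then Φ((−4 + 1.5)/3.5) = 23.8% at the stated cut-off and Φ((−4.348 + 1.5)/3.5) = 20.8% at the shifted one. Assumed mean/SD pairs from −1/3 to −2/4 also give a drop of about 3 percentage points.
- Cardiovascular rate: an illustrative 5 events per 100 calendar patient-years would read 5 × 336 / 365.25 = 4.60 per 100 study years, 8.0% lower.

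**What does not move.** Changing the unit multiplies every subject's time by one constant. The order of events and the risk sets stay the same, so the log-rank statistic and the Cox hazard ratio are unchanged. Exposure-adjusted rates already use 365.25.

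**The case against.** The strongest reply is that this is a declared convention and not a slip. The 28-day month is the protocol's own definition, the SAP's visit labels follow it, and 365.25 is reserved for patient-years. Much of this stands. A study month of 28 days is not wrong where it names a visit or sets a visit-based rule. The Month 18 per-protocol criterion of 15 months of treatment (Section 3.4.1) shows why: it means 15 × 28 = 420 days, and 30.4375-day months would make it 457 days. That is close to the opening of the Month 18 visit window, six weeks before day 504, at day 462. Replacing the 28-day month everywhere would do harm.

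A reader might infer that every follow-up or event time in the report is inflated. The documents do not support that. Component times are in days, exposure is in days and weeks, and exposure-years and pruritus patient-years use 365.25. No visible efficacy table is specified in 336-day years.

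A reader might also infer that 5-year event rates will be misread. The visible SAP plans Kaplan-Meier percentiles and no event rate at a landmark year.

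Finally, it is fair to say that an annualised rate could fall under the patient-year rule and not the study-related one. Under-counting of rapid eGFR decliners is therefore conditional. What remains is that Appendix A is the governing text for any output in years that has no divisor of its own, and it does not say which of its two years applies.

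**Conclusion.** The point holds for any study-related duration expressed in years under Appendix A: it reads 8.7% longer than calendar time and does not tie to the patient-year rates beside it. That follows from the stated rule without further assumption. For the annualised eGFR change and the annualised cardiovascular rate the effect is conditional on their following the 336-day rule. In that case the eGFR cut-off is 4.35 per calendar year, and the cardiovascular rate is 8.0% low. The figure of about 3 percentage points for rapid decliners rests on assumed slope distributions and is only an indication.

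It would be wrong to read this as a threat to the primary analysis; the log-rank tests, hazard ratios and event counts are the same in either unit. It is a defect in descriptive reporting and in two safety summaries, worth correcting because the trial runs about 10 years and the correction is small. One limit: SAP Sections 3.1 to 3.3 are not in the text available for this review, so the time units used there could not be checked.

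**What to change.** - In SAP Appendix A, use 365.25 days per year for every duration or rate expressed in years, and remove the 336-day year.
- Name 365.25 as the divisor for the annualised cardiovascular event rate in Section 10.4.9.1 and for the annualised eGFR change in Section 10.5.6.
- State the time unit for the Kaplan-Meier summaries in Sections 4, 6.4.4.2 and 10.4. If times are shown in months, either divide by 30.4375 or label them as 28-day months.
- Keep the 28-day month for visit names, visit windows, visit-based exposure categories and visit-based thresholds such as the 15-month per-protocol rule, and say so in Appendix A.

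The cost is a few lines of SAP text, one programming constant and a check of table and figure labels. Follow-up reported in years will read about 8% shorter than under the present rule (336 / 365.25 = 0.920). Times shown in 30.4375-day months will no longer match the visit names (Month 18 is 504 days, or 16.6 calendar months), so a footnote is needed where both appear.
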